2.3.1 Risk Assessment

The important identified and potential risks, as well the identified risk of infusion-related reaction (IRRs) were analyzed in depth based on a pooled dataset of $N = 765$ participants who received bintrafusp alfa monotherapy at 12,00 mg once every 2 weeks.

Table 2 Bintrafusp alfa - Identified and Potential Risks with Mitigation Strategies

Identified and Potential Risks of Clinical Significance	Summary of Data/Rationale for Risk	Mitigation Strategy
Study Intervention: Bintrafusp alfa		
Important Identified Risks:		
Immune-related adverse events ^a (irAEs): 
• Immune-related pneumonitis• Immune-related hepatitis• Immune-related colitis• Immune-related nephritis and renal dysfunction• Immune-related endocrinopathies: thyroid disorders, adrenal insufficiency, Type 1 diabetes mellitus, pituitary disorders• Immune-related rash• Other immune-related events (myositis, myocarditis, encephalitis)	In general, immune-related adverse events (irAEs) are known class effects of anti-PD-1/anti-PD-L1 anticancer immunotherapies (Postow 2018) and have been carefully monitored in the bintrafusp alfa clinical studies. irAEs of different nature have occurred in patients receiving bintrafusp alfa in the pooled monotherapy studies and these irAEs have been classified as important identified risks.	Management of irAEs and instructions for study treatment discontinuation or interruption in case of irAEs is described in Section 8.3.6.2 . Regular laboratory tests on parameters indicative for autoimmune disorders, such as thyroid stimulating hormone (TSH), will be performed as detailed in the Schedule of Activities (see Table 1).

Identified and Potential Risks of Clinical Significance	Summary of Data/Rationale for Risk	Mitigation Strategy
Human transforming growth factor β (TGF β) inhibition mediated skin reactions ^a	
TGFβ inhibition mediated skin reactions are important identified risks because neutralization of TGFβ by bintrafusp alfa may induce the development of skin lesions such as hyperkeratosis, keratoacanthoma, cutaneous squamous cell carcinoma (Lacouture 2015). Such skin lesions have indeed been observed in the clinical studies with bintrafusp alfa, but not in patients treated with the anti-PD L1 antibody avelumab. Thus, it is plausible that skin tumors observed in patients treated with bintrafusp alfa may be related to the TGFβ signal pathway inhibition.
	
Monitoring will include skin assessments as defined in the Schedule of Activities (see Table 1).
 
Management of TGFβ inhibition mediated skin reactions is described in Section 8.3.6.3.

Anemia	
Anemia is considered an important identified risk. Toxicological findings with bintrafusp alfa in cynomolgus monkey indicated a decrease in hemoglobin, red blood cell count, and hematocrit. This decrease was fully reversible or showed trend towards recovery after treatment discontinuation. These nonclinical findings were also observed in clinical studies. The mechanism for the effect remains to be fully elucidated, however, the occurrence of hemorrhages may contribute to the observed effect.
	
Management of anemia is described in Section 8.3.6.4.

Bleeding adverse events	
Bleeding adverse events are considered important identified risk. Participants treated with bintrafusp alfa were commonly reported with mild to moderate mucosal adverse events such as epistaxis, hemoptysis, gingival bleeding and hematuria, and in lower frequencies, with Grade ≥ 3 hemorrhages including tumor bleeding. Other TGFβ inhibitors like fresolimumab are also known to be associated with bleeding (Morris 2014; Vincenti 2017). No bleeding events were observed during the nonclinical studies with bintrafusp alfa.
	
Management of bleeding adverse events is described in Section 8.3.6.5.

Identified Risks		
Infusion-related reactions	
Infusion-related reactions (IRRs) are known class effects of monoclonal antibodies including anti PD-L1 antibodies and have been observed in the clinical studies with bintrafusp alfa. However, the frequency and severity of IRRs was relatively low, and no premedication is required to prevent the occurrence of IRRs. Therefore, IRRs are classified as identified (non-important) risk.
	
Special precautions and management of IRRs and immediate hypersensitivity reactions are described in Section 8.3.6.1.

Important Potential Risks		

Identified and Potential Risks of Clinical Significance	Summary of Data/Rationale for Risk	Mitigation Strategy
Immune-related adverse events (irAEs) 
 • Guillain-Barré syndrome • Uveitis • Pancreatitis • Myasthenia gravis/myasthenic syndrome 	irAEs like Guillain-Barré syndrome, uveitis, pancreatitis and myasthenia gravis/myasthenic syndrome have not been observed for bintrafusp alfa in the pooled monotherapy studies and are therefore considered as important potential risks, as these are known risks of the therapeutic drug class of anti-PD-1/anti-PD-L1 antibodies including avelumab.	Management of irAEs and instructions for study treatment discontinuation or interruption in case of irAEs is described in Section 8.3.6.2 .
Impaired wound healing	Impaired wound healing is considered as an important potential risk (a theoretical risk based on literature findings) for bintrafusp alfa, given the role of TGF β in wound healing, repair of skin and other tissue injuries (Pakyari 2013).	Management should be discussed with the Medical Monitor for participants requiring surgery on study. It is recommended to hold study intervention for approximately 4 weeks post major surgery for observation. Postoperative wound healing will be closely monitored.
Embryofetal toxicity	Embryofetal toxicity is a known risk of anti-PD-1/anti-PD-L1 antibodies, and therefore considered as important potential risk for bintrafusp alfa. Animal models link the PD-1/PD-L1 signaling pathway with maintenance of pregnancy through induction of maternal immune tolerance to fetal tissue.	An appropriate contraception warning is provided as part of the inclusion criteria. Participants with pregnancy or in lactation are prohibited from enrolling in bintrafusp alfa clinical trials and adequate contraceptive measures are recommended during the study to minimize or eliminate the potential risk to the developing fetus.

for any serious events, an SAE Report Form has to be used (see [Section 8.3.4](#)).

2.3.2 Benefit Assessment

Participants who will be enrolled in the rollover study to continue bintrafusp alfa treatment have been receiving bintrafusp alfa for a prolonged period of time in the parent study without toxicities requiring permanent treatment discontinuation, while experiencing clinical benefit from the treatment.

The clinical activity of bintrafusp alfa is further summarized in the IB.

2.3.3 Overall Benefit/Risk Conclusion

Participants enrolled in parent protocols with bintrafusp alfa treatment underwent benefit/risk assessments and, by means of their eligibility to participate in this rollover study, have an expected overall positive benefit from continuation or reinitiation of bintrafusp alfa treatment. Given the observed clinical activity of bintrafusp alfa in patients with a number of tumor types and the manageable safety profile observed in more than 700 participants in the Phase I and Phase II studies, the benefit/risk assessment is considered favorable to conduct this study.

3 Objectives and Endpoints

Table 3 Objectives and Endpoints

Objectives	Endpoints
Primary	
To evaluate clinical safety of bintrafusp alfa in participants with solid tumors who continue treatment after completion of the primary/main analyses in parent bintrafusp alfa studies	Occurrence of AEs and treatment-related AEs, starting from baseline in parent study
Secondary	
To evaluate clinical efficacy of bintrafusp alfa based on OS	OS, starting from baseline in parent study

AE = adverse event **CCI**; OS = overall survival **CCI**;

RECIST v1.1 = Response Evaluation Criteria in Solid Tumors Version 1.1.

4 Study Design

4.1 Overall Design

Study Design	Open-label, single arm, rollover
Control Method	None
Single or Multicenter	Multicenter
Control Group	Not applicable
Study Population Type	
Patients with solid tumor; see Sections 5.1 and 5.2.
 
Participants can be transferred from their respective parent bintrafusp alfa study to this rollover study once the primary/main analysis in the parent study has been completed or after discontinuation of study before primary/main analysis has been completed. Participants may also be transferred upon Sponsor decision in case the parent study is terminated for any reason as specified in the parent study protocol and there is a medical need for participants to continue to be treated with bintrafusp alfa that cannot be otherwise supplied. The final decision whether to transfer participants from the parent study rests with the Sponsor.
 
A full list of bintrafusp alfa clinical studies from which participants may be potentially enrolled after completion of the primary analysis or after discontinuation of study before primary/main analysis is provided in Appendix 10.

Level and Method of Blinding	Open-label
Bias Minimalization Method(s)	Not applicable

Study Intervention Assignment Method	
For participants who are continuing treatment with bintrafusp alfa and were previously assigned to a bintrafusp alfa dose based on body weight (i.e., a mg/kg dose) in a parent protocol, the Sponsor recommends switching to a flat dose of bintrafusp alfa 1200 mg every 2 weeks as they enroll in the rollover study, after consultation with the Sponsor Medical Lead. However, participants still on active treatment in their respective parent study may, if considered appropriate by the Investigator, opt to continue treatment at their ongoing dose level as they enter this rollover study, with treatment as follows:
 
• Bintrafusp alfa administered on Day 1 of a 2-week cycle at the dose specified based upon the participant's parent protocol and treatment assignment. 
OR
 
• Bintrafusp alfa administered on Day 1 of a 3-week cycle at a dose of 2400 mg. 
Participants who are entering the rollover study after discontinuation of treatment in a parent study will reinitiate bintrafusp alfa as a monotherapy following the same treatment schedule as specified in their original parent protocol. These participants will reinitiate treatment as either:
 
• Bintrafusp alfa administered on Day 1 of a 2-week cycle at a dose of either 1200 or 2400 mg 
OR
 
• Bintrafusp alfa administered on Day 1 of a 3-week cycle at a dose of 2400 mg. 
Restarting treatment as a combination will not be allowed

Involvement of Special Committee(s):	No.
Total Duration of Study Participation per Participant	All participants in this rollover study will be treated with bintrafusp alfa until meeting criteria for discontinuation (see Section 7.1), until study intervention is commercially accessible and provisioned via marketed product, or until end of study (see Section 4.4). The study also includes a 5 years survival follow-up after last dose of the study treatment.
Provisions for Study Extension or Entry into Rollover Studies	This is a rollover study and it is designed to provide continuous access to treatment with bintrafusp alfa for eligible participants from ongoing bintrafusp alfa parent studies, and to collect long-term safety and efficacy data.
Adaptive Aspects of Study Design	Not applicable

4.2

Scientific Rationale for Study Design

Although not yet approved in any country, bintrafusp alfa has demonstrated meaningful clinical activity across various tumor types and treatment settings. In recent years checkpoint inhibitors have been increasingly used in clinical practice based on superior efficacy and manageable safety profile. Regardless of the tumor type or previous anticancer treatments, responses with bintrafusp alfa appear durable in nature, including ongoing responses > 1 year in several of the cohorts in parent studies. Overall, many responses were still ongoing at the time of database lock of parent studies.

Enrollment in this study will provide continuous access to bintrafusp alfa treatment for participants from parent studies who may experience long-term clinical benefit. Collection of safety data for these participants will provide valuable information to physicians regarding the safety of prolonged treatment with bintrafusp alfa. Participants to be enrolled in this study have been on active bintrafusp alfa treatment without major toxicities requiring treatment discontinuation; therefore, from a long-term perspective it is considered appropriate to continue collection of treatment-related AEs.

Overall survival is the most reliable efficacy endpoint in oncology studies to demonstrate treatment benefit in cancer subjects. Long-term OS data collection will be continued for participants in this study to further support clinical development of bintrafusp alfa.

4.2.1

Participant Input into Design

Not applicable.

4.3

Justification for Dose

In this rollover study, the doses and treatment schedules for bintrafusp alfa (administered as an intravenous [IV] infusion) were selected based on those used in the parent studies and include the following:

- On Day 1 of a 2-week cycle at either a) the flat dose of 1200 mg or b) the dose specified based upon the participant's parent protocol and treatment assignment.
- On Day 1 of a 3-week cycle at a flat dose of 2400 mg.

For participants who are continuing treatment with bintrafusp alfa and were previously assigned to a bintrafusp alfa dose based on body weight (i.e., a mg/kg dose) in a parent protocol, the Sponsor recommends switching to a flat dose of bintrafusp alfa 1200 mg every 2 weeks as they enroll in the rollover study, in consultation with the Sponsor Medical Lead. However, participants still on active treatment in their respective parent study may, if considered

appropriate by the Investigator, opt to continue treatment at their ongoing dose level as they enter this rollover study.

Participants who are entering the rollover study after discontinuation of treatment in a parent study will restart bintrafusp alfa as a monotherapy at either 1200 mg or 2400 mg following the same treatment schedule as specified in their original parent protocol.

These doses for bintrafusp alfa were selected based on safety/tolerability, pharmacokinetics (PK), pharmacodynamics (PD-L1 target occupancy in peripheral blood mononuclear cell and TGF β plasma concentrations), and efficacy data in the parent studies, as well as population PK and exposure-response modeling and simulations.

The 1200 mg every 2 weeks dose selection was based on the recommended Phase II dose for bintrafusp alfa, and the 2400 mg every 3 weeks dose selection was based on modeling and simulation data indicating this dose maintains target efficacious $C_{trough,ss}$ of bintrafusp alfa. Additionally, assessment of potential PK interactions and overlapping toxicities with chemotherapies was conducted to support 2400 mg every 3 weeks dose of bintrafusp alfa in the parent combination studies. Since most chemotherapies are administered every 3 weeks, the same dosing interval for bintrafusp alfa was preferred for convenience and compliance in the parent combination studies.

Refer to the IB for additional details and data for dose justification.

4.4 End of Study Definition

A participant has completed the study if he/she has completed all study parts, including the last visit or the last scheduled procedure shown in [Section 1.3](#).

The end of the study is defined as the date of the last scheduled procedure shown in the SoA for the last participant in the study and when there are no other eligible parent studies ongoing from which participants could enroll in this rollover study.

The survival follow-up will continue until up to a maximum of 5 years after the last participant receives the last dose of bintrafusp alfa. This duration may be shortened at the discretion of the Sponsor for any given indication.

The Sponsor may terminate the study at any time once access to study intervention for participants still benefiting is provisioned via marketed product or another mechanism of access as appropriate. See also [Appendix 2](#) for study and site closure.

5 Study Population

The criteria in [Sections 5.1](#) and [5.2](#) are designed to enroll only participants, who are appropriate for the study; thereby, ensuring the study fulfills its objectives. All relevant medical and nonmedical conditions are considered when deciding whether a participant is suitable for this study.

Prospective approval of protocol deviations to inclusion and exclusion criteria, also known as protocol waivers or exemptions, is not permitted.

Before performing any study assessments that are not part of the participant's routine medical care, the Investigator will confirm that the participant or the participant's legal representative (where allowed by local laws and regulations) has provided written informed consent, as indicated in [Appendix 2 Study Governance](#).

5.1 Inclusion Criteria

Participants are eligible to be included in the study only if all the following criteria apply:

Category	Criterion
Age	1. Are ≥ 18 years of age at the time of signing the informed consent. In Japan, if a participant is at least 18 but < 20 years of age, written informed consent from his/her parent or guardian will be required in addition to the participant's written consent.
Type of Participant and Disease Characteristics	
2. Are participants currently enrolled in an eligible bintrafusp alfa parent study (see Appendix 10) where the primary/main analysis has been completed or after discontinuation of study before primary/main analysis has been completed and who:
 
• Are currently on active bintrafusp alfa treatment (alone as a monotherapy or following discontinuation of other combination treatment agents) in the parent study and without treatment interruption at the time of rollover study enrollment, OR.• Experienced a confirmed CR, PR, or SD in an eligible parent study, discontinued bintrafusp alfa treatment according to the parent study protocol, and subsequently developed disease progression and are willing to re-start bintrafusp alfa treatment deemed potentially beneficial by the participants' physicians OR• Discontinued from bintrafusp alfa treatment in an eligible parent study due to an AE(s) that was subsequently well controlled or completely resolved after stopping therapy, provided that the parent study protocol permits reinitiation of bintrafusp alfa if a participant discontinued treatment due to toxicity and these participants are willing to re-start bintrafusp alfa treatment deemed potentially beneficial by the participants' physicians. Participants who have had AEs requiring permanent treatment discontinuation, like certain irAEs or certain bleeding events (see Sections 6.8 and 2.3.1 for details) are excluded from participation in this Rollover study. 
Note: Prior to treatment reinitiation, the Investigator, in consultation with the study Medical Monitor as needed, must confirm that the benefit of reinitiating treatment outweighs any risk involved, including that which led to the prior treatment discontinuation. For participants with only SD at the time of discontinuation, the Investigator should confirm that no other reasonable treatment options are available.
 
• Have completed End of treatment (EoT) assessment of a parent study.

Category	Criterion
Sex and Contraception/Barrier Requirements	
3. The allowed sex/sexes for the study:
 
• Male• Female 
The investigator confirms that each participant agrees to use appropriate contraception and barriers, if applicable. The contraception, barrier, and pregnancy testing requirements are below. For female participants of childbearing potential or for male participants who have female partners of childbearing potential, the following applies:
 
Participants on active treatment must agree to continue to use highly effective contraception (i.e., methods with a failure rate of less than 1% per year; see Appendix 3) for both male and female participants if the risk of conception exists (Note: The effects of the study intervention on the developing human fetus are unknown (refer to Section 2.3.1); thus, women of childbearing potential and men must agree to use highly effective contraception as stipulated in national or local guidelines). Highly effective contraception must be used 28 days prior to the first study intervention administration, for the duration of study intervention, and at least for 2 months (for female participants) or 4 months (for male participants) after stopping study intervention. Should a woman become pregnant or suspect she is pregnant while she or her partner is participating in this study, the treating physician should be informed immediately.

Informed Consent	4. Capable of giving signed informed consent, as indicated in Appendix 2 , which includes compliance with the requirements and restrictions listed in the informed consent form (ICF) and this protocol.

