Appendix 3 Contraception

Woman of Childbearing Potential

Definitions:

Woman of Childbearing Potential (WOCBP)

A woman is considered fertile following menarche and until becoming postmenopausal unless permanently sterile, as specified below.

If fertility is unclear (e.g. amenorrhea in adolescents or athletes) and a menstrual cycle cannot be confirmed before the first dose of study intervention, consider additional evaluation.

A WOCBP is **not**:

1. Premenarchal
2. A premenopausal female with one of the following:
 - Documented hysterectomy
 - Documented bilateral salpingectomy
 - Documented bilateral oophorectomy

Documentation can come from the site personnel's review of the female's medical records, medical examination, or medical history interview.

For a female with permanent infertility due to an alternate medical cause other than the above, (e.g. mullerian agenesis, androgen insensitivity), Investigator discretion applies to determine study entry.

3. A postmenopausal female
 - A postmenopausal state is defined as no menses for 12 months without an alternative medical cause.
 - A high follicle-stimulating hormone (FSH) level in the postmenopausal range may be used to confirm a postmenopausal state in a female not using hormonal contraception or hormonal replacement therapy (HRT). However, in the absence of 12 months of amenorrhea, more than 1 FSH measurement is required in the postmenopausal range.
 - A female on HRT and whose menopausal status is in doubt will be required to use one of the non-estrogen hormonal highly effective contraception methods if she wishes to continue her HRT during the study. Otherwise, she must discontinue HRT to allow confirmation of postmenopausal status before study enrollment.

Contraception Guidance:

CONTRACEPTIVES ALLOWED DURING THE STUDY INCLUDE:

Highly Effective Methods That Have Low User Dependency

- Implantable progestogen-only hormone contraception associated with inhibition of ovulation*
- Intrauterine device
- Intrauterine hormone-releasing system
- Bilateral tubal occlusion
- Vasectomized partner: a highly effective contraceptive method provided that the partner is the sole sexual partner of a WOCBP and the absence of sperm has been confirmed. Otherwise, use an additional highly effective method of contraception. The spermatogenesis cycle is approximately 90 days.

* Not approved in Japan

Highly Effective Methods That Are User Dependent

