- Combined (estrogen- and progestogen-containing) hormonal contraception associated with inhibition of ovulation
 - Oral
 - Intravaginal*
 - Transdermal*
 - Injectable
- Progestogen-only hormone contraception associated with inhibition of ovulation
 - Oral
 - Injectable*
- Sexual abstinence: a highly effective method **only** if defined as refraining from intercourse during the entire period of risk associated with the study intervention. The reliability of sexual abstinence is evaluated in relation to the duration of the study.
- * Not approved in Japan

Acceptable Methods

- Progestogen-only oral hormonal contraception where inhibition of ovulation is not the primary mode of action
- Male or female condom with or without spermicide**. Male condom and female condom cannot be used together (due to risk of failure with friction)
- Cervical cap*, diaphragm, or sponge with spermicide*
- A combination of male condom with either cervical cap, diaphragm, or sponge with spermicide (double-barrier methods)

* Not approved in Japan

** Not available in Japan

Contraceptive use by men or women is consistent with local regulations regarding the use of contraceptive methods for those participating in clinical studies.

Highly effective methods have a failure rate of < 1% per year when used consistently and correctly. Typical use failure rates differ from those when used consistently and correctly.

If locally required, in accordance with Clinical Trial Facilitation Group guidelines, acceptable contraceptive methods are limited to those which inhibit ovulation as the primary mode of action.

Acceptable methods are considered effective, but **not** highly effective (i.e. have a failure rate of $\geq 1\%$ per year). Periodic abstinence (calendar, symptothermal, post-ovulation methods), withdrawal (coitus interruptus), spermicides only, and lactational amenorrhea method (LAM) are **not** acceptable methods of contraception.

Appendix 4 Adverse Events: Definitions and Procedures for Recording, Evaluating, Follow-up, and Reporting

AE Definition

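### Appendix 3 lists as allowed four contraceptive options that inclusion criterion 3 rules out

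*Protocol*

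**What the plan says.** Protocol Section 5.1, criterion 3, covers female participants of childbearing potential and male participants with partners of childbearing potential. It asks for "highly effective contraception (i.e., methods with a failure rate of less than 1% per year; see Appendix 3"). The requirement starts 28 days before the first dose, runs through treatment, and continues for at least 2 months (women) or 4 months (men) after stopping.

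Appendix 3 is where the criterion sends the reader. Its method list stands under the heading "CONTRACEPTIVES ALLOWED DURING THE STUDY INCLUDE" and has three groups:

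- highly effective methods with low user dependency;
- highly effective methods that depend on the user;
- Acceptable Methods, with four entries: "Progestogen-only oral hormonal contraception where inhibition of ovulation is not the primary mode of action"; "Male or female condom with or without spermicide"; cap, diaphragm or sponge with spermicide; and a male condom combined with one of these barriers.

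The closing notes of the appendix define highly effective as a failure rate below 1% per year. They add that "Acceptable methods are considered effective, but not highly effective", with a failure rate of 1% or more per year. One conditional restriction on the third group follows: "If locally required, in accordance with Clinical Trial Facilitation Group guidelines, acceptable contraceptive methods are limited to those which inhibit ovulation" as their main mode of action. The notes also name methods that are not acceptable at all, such as periodic abstinence and withdrawal.

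Table 2 (Section 2.3.1) classes embryofetal toxicity as an important potential risk. In its mitigation column it says: "An appropriate contraception warning is provided as part of the inclusion criteria".

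**The concern.** The criterion sets one standard, and the appendix it cites lists as allowed a group of methods below that standard. A site choosing a method from the appendix could accept a woman of childbearing potential on a barrier method alone, or a male participant relying on condoms, and believe that it had followed the protocol.

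Two things are at stake. The first is safety: the protocol states that effects on the human fetus are unknown, and contraception is the preventive part of the mitigation. Pregnancy is an exclusion, testing is scheduled, and drug is withheld from a participant known to be pregnant. After enrolment, though, those steps detect a pregnancy and respond to it; they do not prevent one. The second is eligibility. Prospective approval of deviations from the criteria, "also known as protocol waivers or exemptions, is not permitted" (opening of Protocol Section 5), and SAP Section 10.2.1 counts dosing someone who fails an enrolment criterion as an important protocol deviation. The appendix could therefore lead a site into a deviation that the protocol gives no means of approving.

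**Working it through.** No power, sample size or error-rate calculation is involved. The check sets the two texts side by side.

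| Item | Criterion 3 (Section 5.1) | Appendix 3 |
|---|---|---|
| Standard | Highly effective only | Three groups under one heading of allowed methods |
| Threshold for highly effective | Below 1% per year | Below 1% per year, with consistent and correct use |
| Status of the third group | Not mentioned, so excluded by the threshold | Listed as allowed; described as not highly effective |
| Failure rate of the third group | Not given | 1% or more per year |

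1. **Same definition.** Both places use a failure rate below 1% per year, so a difference in the meaning of highly effective does not explain the mismatch.
2. **No overlap.** Below 1% and 1% or more are mutually exclusive, so 4 of the 4 entries in the third group fail criterion 3.
3. **Is the third group limited elsewhere?** The only limit in Appendix 3 applies where local rules require it. That leaves the group in place where they do not. No sentence says that these methods fall short of criterion 3 or may only be added to a highly effective method.
4. **What the layout implies.** The appendix separately names methods that are not acceptable, which puts the third group on the permitted side of the line. Condoms, caps, diaphragms and sponges appear only in the third group, so a participant relying on one of them finds it only there.
5. **Reach.** The Synopsis expects at least 10 participants. The documents do not say how many are women of childbearing potential or men with such partners, so the number concerned could be anywhere from none to all of them.
6. **What remains if a site gets it wrong.** Table 1 schedules pregnancy tests on Day 1 of every other cycle and at the 30-day visit. On 2-week cycles that is one test every 2 × 2 = 4 weeks; on 3-week cycles, every 2 × 3 = 6 weeks. Table 1 schedules no testing of male participants' partners.

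**The case against.** The strongest reply is that the rule gives only one answer. Criterion 3 repeats its requirement for highly effective contraception and states the threshold. Appendix 3 uses the same threshold, labels two groups as highly effective and says outright that the third is not. A site that arrives from criterion 3 looking for highly effective methods will find the matching headings. On this view the heading lists what may be used, not what is enough for eligibility, and the third group is there because criterion 3 also speaks of barriers where applicable. Criterion 3 also refers to national or local guidelines, and the appendix defers to local regulations. No endpoint, analysis set or estimate depends on any of this.

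Much of that stands. A strict reading of criterion 3 does exclude the third group, the appendix labels the group honestly, and a careful site would get it right. There is no evidence that any site has misread it or will. What does not stand is the reading of allowed as supplementary only, because neither section says so. The references to local guidelines do not supply it either: they do not say that a method failing at 1% or more per year is insufficient on its own, and the one conditional restriction reads as though the group is otherwise usable.

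**Conclusion.** The point holds. Appendix 3 lists as allowed four options that criterion 3 excludes by the protocol's own 1% threshold, and it does not resolve the conflict. Both texts are current.

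The claim is limited: a site could misapply the criterion, not that it must. The reach is small (at least 10 participants, with an unstated number to whom the rule applies), and the statistical analysis is untouched. Table 2 sets no failure-rate level and is not itself contradicted. The inconsistency should still be corrected, because it bears on an eligibility criterion that serves as mitigation for an important potential risk. The conclusion rests only on the wording of the two sections and needs no outside figure.

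**What to change.** Either of two edits to Appendix 3 is enough:

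- remove the Acceptable Methods group from the list of allowed contraceptives; or
- keep it and add one line: these methods do not satisfy inclusion criterion 3 and may be used only in addition to a highly effective method.

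If the group is removed, the closing notes that refer to it should be tidied to match. Criterion 3 and Table 2 need no change.

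The cost is a deletion or a single sentence at the next amendment. The one practical downside is that a participant using only a method from the third group would have to add or switch to a highly effective one, which criterion 3 already requires.
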